15.2 Trial analysis sets

A per protocol analysis set will be used as the main efficacy measure for the analysis of the endpoints at week 16.

The per protocol analysis set will be defined by excluding subjects for whom any of the following conditions apply:

- major protocol violations (e.g. did not receive treatment with investigational medicinal product)
- are known to have initiated prohibited medicine (section 11.6) during the trial
- follow-up FDG-PET/CT not completed

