15.3 Statistical analysis

15.3.1 Disposition of subjects

For all randomised subjects the reasons for leaving the trial in the follow-up period will be presented by last visit attended and last week completed for each group, respectively.

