15.4 Analysis of endpoints

15.4.1 Analysis of primary endpoints

The primary endpoint, change in the average of maximum TBR values (MeanTBR_{max}) of the entire aorta from baseline to week 16, will be analysed for the per protocol analysis set. The endpoint will be analysed using a repeated measurements model.

Estimates and 95% confidence intervals (CIs) or standard deviations (SDs) for the change in meanTBR_{max} and treatment differences will be presented. Values for the entire aorta and aortic subsegments will be presented. The difference in efficacy between treatment groups will be analysed. The null hypothesis of no difference in change in meanTBR_{max} between

Trial ID (EudraCT No.): 2017-003697-14	Date: 23.02.2018	Page Version 2.3
---	------------------	---------------------

brodalumab and placebo will be tested against the two-sided alternative that there is a difference.

If applicable, a supportive multivariate analysis will be performed to test the effect of the continuous covariates age, body mass index, statin treatment and categorical variables gender and smoking status on the difference in vascular FDG uptake at week 16.

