15.4.2 Analysis of secondary endpoints

The 4 secondary efficacy endpoints evaluate the impact of 16 weeks of treatment on (I) change in SLR, (II) change in the average of maximum TBR values (MeanTBR_{max}) of each aortic subsegment (ascending, aortic arch, descending, suprarenal, and infrarenal aorta), (III) association between change in PASI and change in aortic wall FDG-uptake, (IV) association between change in PASI and change in SLR.

These endpoints will be evaluated by testing the hypothesis of no difference between brodalumab and placebo. The endpoints will be analysed and presented for the per protocol analysis set.

The change from baseline to Week 16 in SLR and aortic subsegment FDG-uptake are continuous endpoints and will be analysed using a repeated measurements model.

If applicable, a supportive multivariate analysis will be performed as described in section 12.4.1.

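### The between-arm tests of the primary endpoint, SLR and aortic subsegments rest on a per-protocol set that can drop randomised subjects who have both scans

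*Protocol*

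**What the plan says.** Protocol section 15.2 defines one efficacy set: "A per protocol analysis set will be used as the main efficacy measure for the analysis of the endpoints at week 16". A subject is left out if any one of three conditions applies. The first is "major protocol violations (e.g. did not receive treatment with investigational medicinal product"; the second covers those who "are known to have initiated prohibited medicine (section 11.6) during the trial"; the third is a missing follow-up scan.

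For the primary endpoint, section 15.4.1 says that it "will be analysed for the per protocol analysis set. The endpoint will be analysed using a repeated measurements model", and that the null hypothesis of no difference in change between "brodalumab and placebo will be tested against the two-sided alternative that there is a difference". For the secondary endpoints, section 15.4.2 says: "These endpoints will be evaluated by testing the hypothesis of no difference between brodalumab and placebo" and "The endpoints will be analysed and presented for the per protocol analysis set". The supportive multivariate analysis in both sections adds covariates and leaves the set unchanged.

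All randomised subjects are named twice, neither time for efficacy. Section 15.3.1 reads "For all randomised subjects the reasons for leaving the trial in the follow-up period will be presented", and section 15.3.2 covers baseline tables.

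**The concern.** This is a randomised, double-blind, placebo-controlled comparison tested two-sided for a difference. Its validity comes from comparing the groups as randomised. A missing week-16 scan is a missing-data matter, but the other two exclusion rules do not depend on the scans. They act on events after randomisation that may be related to arm and to response.

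The protocol itself supplies a plausible link. Section 8.9 foresees flare in the placebo group during the study period. The prohibited list in section 12.6 includes other topical psoriasis treatments such as calcipotriol, so a topical started for a flare can be enough to exclude a subject. Section 8.5 hypothesises that effective psoriasis treatment lowers aortic inflammation, so exclusion that follows skin worsening could be related to TBR change. The major-violation rule is open-ended, with a single example.

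At stake are the primary test, the SLR test and the subsegment tests. With no all-randomised efficacy analysis named, a reader could not separate an effect of treatment from an effect of the exclusions. Secondary endpoints III and IV are associations with PASI change and are less affected.

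**Working it through.** **1. The planned size reproduces.** Inputs from section 15.1: means 2.4 and 2.1 (difference 0.30), SD 0.35, two-sided alpha 0.05, power 80%. The normal formula gives n = 2 × (1.960 + 0.842)² × (0.35/0.30)² = 21.4, so 22 per arm as stated. Adding 3 per arm for dropout gives 25. Sections 15.1 and 10.2 describe that allowance as dropout; no provision is stated for excluding scanned subjects.

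**2. Assumptions.** The protocol gives no SD of change, number of exclusions or link between exclusion and TBR change.
- SD of change = 0.35 × √(2(1 − ρ)), with ρ the within-subject correlation: 0.35 at ρ = 0.5, 0.28 at ρ = 0.68, 0.221 at ρ = 0.8.
- Correlation r between the tendency to be excluded and TBR change: 0.2 to 0.7. The protocol supports no particular value, and section 8.3 gives mixed evidence on a skin–aorta link.
- The subjects with the highest exclusion tendency are removed, which is a strong form of selection. A two-sample t-test on change stands in for the repeated-measurements model.

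**3. Shift in the estimated difference.** Shift = r × SD × (mean standardised score of those left after removing the top k of 25). That mean is −0.151 for k = 2, −0.215 for k = 3, −0.276 for k = 4 and −0.335 for k = 5.

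| Removed | Low (r 0.2, SD 0.221) | High (r 0.7, SD 0.35) | Share of 0.30 |
|---|---|---|---|
| 3 placebo | 0.010 | 0.053 | 3–18% |
| 5 placebo | 0.015 | 0.082 | 5–27% |
| 2 brodalumab, 4 placebo: (0.276 − 0.151) × r × SD | 0.006 | 0.031 | 2–10% |

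All three shrink the effect. Removing equal numbers by the same mechanism gives no mean shift. The same removals on brodalumab only would inflate the effect by the same amounts.

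**4. False positives favouring brodalumab (simulated, no true effect, nominal 2.5%).** With 5 placebo subjects removed the rate falls to 1.5% (r 0.2) or 0.4% (r 0.7). With 3 brodalumab subjects removed it rises to about 3.5% (r 0.2) or 8% (r 0.7). With 4 removed per arm it is 2.5 to 3.4%.

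**5. Power at a true difference of 0.30.**

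| Per arm | SD 0.35 | SD 0.28 | SD 0.22 |
|---|---|---|---|
| 25 | 84.4% | 96.0% | 99.7% |
| 22 | 79.3% | 93.5% | 99% |
| 20 (unrelated exclusions) | 75.2% | 91.0% | 98.7% |

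Selectively removing 5 placebo subjects from 25 per arm at SD 0.35 takes power from 84% to 73% (r 0.2) or 56% (r 0.7). Part of that is sample size: 25 against 20 with no selection already gives 79.8%, and the rest of the fall is bias. At SD 0.22 power stays at about 99% (r 0.2) or 96% (r 0.7).

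**The case against.** The strongest reply has five parts.

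- *Main does not mean only.* Section 15.2 leaves room for other sets, and an SAP, not seen here, may add one. That is fair, but the protocol fixes the per-protocol set as the main one and names no other for any test. An added set would rank below it.
- *The question is mechanistic.* Section 8.5 asks about IL-17RA blockade, and a prohibited anti-inflammatory could itself alter FDG uptake. This is a good reason for a supportive per-protocol analysis. It does not justify giving up the comparison as randomised for the main test.
- *The routes to exclusion are narrow.* Bland emollient and class II or weaker steroids stay allowed (12.4), the first dose is given on site (12.2), and treatment interruption can be met by postponing the final visit (12.7.5). Blinding (12.3.1) limits exclusion made with knowledge of arm. All of this lowers the likely number of exclusions. It does not stop exclusion that follows a flare.
- *The foreseen direction is conservative.* Placebo flare would shrink the effect, and the protocol describes no mechanism for selective removal on brodalumab. This stands, and no claim of inflation is made.
- *The sizes are assumed, and power does not decide the matter.* This also stands. The illustrations mix bias with lost numbers, and the remedy has a power cost of its own. The case rests on validity.

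**Conclusion.** The concern holds. For the primary endpoint, SLR and the aortic subsegments, the protocol ties the randomised comparison to a set from which scanned subjects can be removed for events after randomisation, and it names no all-randomised efficacy analysis against which to check the result.

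Whether bias would arise, how large it would be and in which direction cannot be known from the protocol. The figures of 3 to 18% (3 placebo subjects removed) and 5 to 27% (5 removed) of the planned 0.30 depend wholly on the assumed SD of change, exclusion counts and correlation. The point must be fixed because it affects the primary test, not because a bias of a given size has been shown.

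**What to change.** In sections 15.2, 15.4.1 and 15.4.2, before unblinding:

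- Make the primary set all randomised subjects, analysed in the arm to which they were randomised, regardless of protocol violations or prohibited medication.
- Fit the planned repeated-measurements model to all available scans, and state the missing-at-random assumption for missing week-16 scans.
- Keep the per-protocol analysis as supportive, and report its exclusions by arm and reason.
- Editorial: the exclusion rule cites section 11.6 (Discontinuation); the prohibited list is in 12.6.

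The cost is wording, with no added scan, visit or procedure. The downside is dilution by non-adherence. With 25 scanned per arm and 2 or 3 brodalumab subjects getting no effect, the expected difference falls to 0.30 × 23/25 = 0.276 or 0.30 × 22/25 = 0.264. Power is then 77% or 73% at SD 0.35, 92% or 89% at SD 0.28, and 99% or 98% at SD 0.22. Changing the set does not cure bias from missing week-16 scans.

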
brodalumab treated psoriasis subjects compared to placebo and whether this change is associated with changes in skin inflammation.
 
To assess the change in soluble inflammatory biomarkers from baseline to week 16 in brodalumab treated psoriasis subjects compared to placebo.
 
To assess whether the change in aortic wall inflammation and/or splenic inflammation is associated with psoriasis-specific genotypes.
 
To assess the change in gene expression and cytokine expression in paired lesional and non-lesional psoriatic skin from baseline to week 16 in brodalumab treated psoriasis subjects compared to placebo.
	
 subcutaneous adipose tissue from baseline to week 16 Association between change in PASI and change in subcutaneous adipose tissue MeanSUV_{max}. Changes in acute phase proteins from baseline to week 16 Correlation between changes in both aortic meanTBR_{max} and SLR and presence of HLA-B*08, HLA-C*06:02, HLA-B*27, HLA-B*38 and HLA-B*39 Changes in gene expression and cytokine expression in skin samples from baseline to week 16 Correlation with changes in mean aortic TBR_{max} and SLR.
---	---

10 Trial design

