- Rescheduled administration of placebo/brodalumab
- Further work-up (e.g. laboratory tests) and concomitant treatment of infection

Patients are instructed to contact the investigator/trial site in case of fever > 38°C within 1 week prior to scheduled FDG-PET/CT. Rescheduling of FDG-PET/CT is at the investigator's discretion.

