15.3.3 Treatment efficacy

Efficacy of brodalumab on skin, nails, and joints compared to placebo will be shown as reduction in PASI, IGA, DLQI, VAS, joint count, and nail count at week 16 for both groups.

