15.4.3 Analysis of other endpoints

Change in acute phase proteins at week 16 between groups and change in abdominal subcutaneous adipose tissue FDG-uptake will be analysed using a repeated measures model. Changes in cytokine expression and gene expression in optional skin samples will be analysed using a repeated measures model. Association between change in PASI and change in subcutaneous adipose tissue as well as the association between change in TBR/SLR and psoriasis-specific genotypes will be computed using applicable correlation coefficients.

Trial ID (EudraCT No.): 2017-003697-14	Date: 23.02.2018	Page Version 2.3
---	------------------	---------------------

16

REFERENCES

2. Christophers E. Psoriasis – epidemiology and clinical spectrum. *Clinical and Experimental Dermatology*. 2001;26(4):314-320.
3. Bowcock AM. The genetics of psoriasis and autoimmunity. *Annu Rev Genomics Hum Genet*. 2005;6:93-122.

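### The week-16 analysis set drops any subject without a second FDG-PET/CT, even for endpoints that do not use the scan, most clearly acute phase proteins

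*Protocol*

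**What the plan says.** Section 15.2 of the protocol defines one efficacy set and gives it general scope: "A per protocol analysis set will be used as the main efficacy measure for the analysis of the endpoints at week 16". Exclusion works on the whole subject: "The per protocol analysis set will be defined by excluding subjects for whom any of the following conditions apply". The three conditions are a major protocol violation, use of prohibited medicine, and "follow-up FDG-PET/CT not completed".

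Sections 15.4.1 and 15.4.2 name this set again for the primary and secondary endpoints. Two other sections report results without naming any set:

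- Section 15.4.3 gives a repeated measures model for "Change in acute phase proteins at week 16 between groups". Section 9.1 lists the matching endpoint: "Changes in acute phase proteins from baseline to week 16".
- Section 15.3.3 says that efficacy on skin, nails and joints will be "shown as reduction in PASI, IGA, DLQI, VAS, joint count, and nail count at week 16".

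All randomised subjects are used only for disposition (15.3.1) and baseline characteristics (15.3.2).

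**The concern.** Whether the second scan was done has no bearing on whether CRP, PASI or a skin sample was obtained. A subject-level exclusion for a missing scan therefore discards valid measurements of other kinds. The repeated measures model for acute phase proteins could, in principle, take in a week-6 value from someone who has no week-16 visit, but the set removes that subject before the model is fitted.

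Two things are at stake for the non-scan endpoints. One is precision, in a trial with only 25 subjects per arm. The other is comparability of the arms, should a missing scan be related to treatment or response. Nothing is lost for scan endpoints, because a subject without a second scan has no change to analyse there.

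**Working it through.** **1. Which endpoints need the scan.** This comes from sections 7, 9.1, 13.4.3, 13.4.4, 15.3.3 and 15.4.3.

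| Measure | Needs second scan? | Scheduled | Set named in its analysis section |
|---|---|---|---|
| Aortic MeanTBRmax, SLR and their associations with PASI | Yes | Weeks 0, 16 | Per protocol |
| Adipose tissue uptake and its association with PASI | Yes | Weeks 0, 16 | None |
| Acute phase proteins | No | Screening, weeks 0, 6, 16 | None |
| PASI, IGA, DLQI, VAS, nail count | No | Screening, weeks 0, 6, 16 | None |
| Skin gene and cytokine expression | No | Baseline and week 6 | None |

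Acute phase proteins are a listed endpoint with change to week 16, so the general rule of 15.2 applies directly. For the 15.3.3 measures the rule applies by inference, because 15.2 defines the only efficacy set. The same holds for skin expression, with one further complication: 9.1 describes change to week 16 while the biopsies are taken at baseline and week 6. That mismatch is a separate matter.

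**2. Whether non-scan data can exist without a scan.** Yes. Bloods and scores at week 6 precede the second scan. Section 11.6 also invites subjects who stop treatment to an early termination visit at which data are collected.

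**3. The plan's own figure.** Section 15.1 assumes means of 2.4 and 2.1, SD 0.35 and alpha 0.05; section 15.4.1 makes the test two-sided.

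n per arm = 2 × (1.960 + 0.842)² × 0.35² / 0.3² = 21.4, rounded up to 22.

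This reproduces the stated 22. Power at 22 per arm is 81.1% by the normal approximation and 79.3% by the t-test. With 3 of 25 lost (12%), 22 / 0.88 = 25, as stated. Section 10.2 says that the allowance covers dropout before the second scan.

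**4. Loss of precision for a non-scan endpoint.** Assume that all 3 unscanned subjects per arm have usable non-scan data. The standard error is then larger by sqrt(25/22) = 1.066, that is 6.6%.

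As an assumed illustration, take an effect with 80% power at 25 per arm (standardised difference 0.81):

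| Dropped per arm | Retained per arm | Standard error ratio | Power |
|---|---|---|---|
| 0 | 25 | 1.000 | 80.0% |
| 1 | 24 | 1.021 | 78.3% |
| 2 | 23 | 1.043 | 76.5% |
| 3 | 22 | 1.066 | 74.6% |
| 5 | 20 | 1.118 | 70.3% |

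**5. Selection, illustration only.** Suppose that the 3 excluded subjects differ by δ from the mean of all 25 in their arm. The mean of the 22 retained then shifts by 3δ/22: 0.07 SD for δ = 0.5 SD and 0.14 SD for δ = 1 SD. The documents give no value for δ.

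**The case against.** Four arguments carry weight.

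- **Selective loss of high CRP values.** A reader might infer that febrile subjects miss the scan and so take their raised CRP out of the analysis. The text does not support this. Section 12.2 says: "Patients are instructed to contact the investigator/trial site in case of fever > 38°C within 1 week prior to scheduled FDG-PET/CT". It then leaves rescheduling to the investigator, and 12.7.5 allows the final visit to be postponed after an interruption of treatment. The protocol provides for a delayed scan and sets out no route by which fever leads to none. Outcome-related selection remains possible, no more.
- **The 6.6% is a ceiling.** Section 15.1 allows for 3 dropouts; it does not predict 3 subjects who are bled and scored but not scanned. Scan, bloods and scores all belong to the same week-16 visit, so many subjects who miss one will miss the others. This stands.
- **The reach is narrow.** Sections 15.3.3 and 15.4.3 do not name the per protocol set, and IGA, DLQI, VAS and the joint and nail counts are not endpoints in 9.1. This stands for the clinical measures and skin expression, where the point is inferential. It does not remove acute phase proteins.
- **A main set does not bar other analyses, and the SAP may add them.** It is true that the protocol does not forbid a supportive analysis. But it has not left the matter open: it fixes a rule with general scope and defines no other efficacy set, so an SAP that follows it inherits the exclusion.

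**Conclusion.** The point holds in a limited form. As written, 15.2 discards usable acute phase protein data because of a missing scan, including week-6 values of subjects who leave later. By inference it does the same for the 15.3.3 measures and skin expression.

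At the protocol's dropout allowance this concerns up to 3 of 25 subjects per arm, and the standard error rises by at most 6.6%. That bound assumes that every unscanned subject has complete non-scan data. The gain from week-6 values further assumes that the repeated measures model includes the week-6 visit, which 15.4.3 does not state.

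The documents do not show that CRP results would be biased, and the point does not touch the primary endpoint or any other scan-based endpoint. It deserves correction because the rule has no rationale for these measures and the change is small.

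**What to change.** In section 15.2, restrict the third exclusion to endpoints that use the scan: MeanTBRmax (whole aorta and subsegments), SLR, adipose tissue uptake, and associations involving any of these. Add that acute phase proteins, the 15.3.3 clinical measures and skin expression are analysed in subjects with a baseline and at least one post-baseline value of that measure, whether or not the second scan was done.

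The exclusions for major violations and prohibited medicine stay as they are under this change; whether they are appropriate is a separate question.

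The cost is a short addition to 15.2 and no new data. The number analysed will differ between scan and non-scan endpoints, so each table must show its own denominator by arm.

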15.3 Statistical analysis

15.3.1 Disposition of subjects

For all randomised subjects the reasons for leaving the trial in the follow-up period will be presented by last visit attended and last week completed for each group, respectively.

15.3.2 Demographics and other baseline characteristics

Descriptive statistics of demographics and other baseline characteristics will be presented for all randomised subjects. The presentations will be by treatment group.

Demographics include age, sex, and race. Other baseline characteristics include height, weight, body mass index, waist circumference, duration of psoriasis, PASI, nail and joint involvement, DLQI, concurrent diagnoses, concomitant medication, and previous psoriasis treatments.

15.3.3 Treatment efficacy

Efficacy of brodalumab on skin, nails, and joints compared to placebo will be shown as reduction in PASI, IGA, DLQI, VAS, joint count, and nail count at week 16 for both groups.

15.4 Analysis of endpoints

15.4.1 Analysis of primary endpoints

The primary endpoint, change in the average of maximum TBR values (MeanTBR_{max}) of the entire aorta from baseline to week 16, will be analysed for the per protocol analysis set. The endpoint will be analysed using a repeated measurements model.

Estimates and 95% confidence intervals (CIs) or standard deviations (SDs) for the change in meanTBR_{max} and treatment differences will be presented. Values for the entire aorta and aortic subsegments will be presented. The difference in efficacy between treatment groups will be analysed. The null hypothesis of no difference in change in meanTBR_{max} between

Trial ID (EudraCT No.): 2017-003697-14	Date: 23.02.2018	Page Version 2.3
---	------------------	---------------------

brodalumab and placebo will be tested against the two-sided alternative that there is a difference.

If applicable, a supportive multivariate analysis will be performed to test the effect of the continuous covariates age, body mass index, statin treatment and categorical variables gender and smoking status on the difference in vascular FDG uptake at week 16.

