10.1 Overall trial design

This is an investigator-initiated, single-center, randomized, double-blind (subjects, investigators, and nuclear medicine specialists and all staff involved in vascular imaging and analysis is blinded to group assignment) prospective, controlled study. Subjects are randomized and matched on sex and age (\pm 5 years) (stratified randomization).

Subjects with moderate-to-severe psoriasis are enrolled consecutively and randomly assigned to either active treatment with brodalumab or placebo during the treatment period. Subjects are entered into a pre-study washout period, if needed, wherein all active anti-psoriatic topical and systemic therapies are discontinued according to pre-specified time frames.

Psoriasis subjects are examined with FDG-PET/CT at baseline and again at end of study after 16 weeks of brodalumab treatment or placebo, respectively.

Baseline investigations include medical history, physical examination, and laboratory tests.

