12.3 Treatment assignment

Subjects who have been found to comply with all the inclusion criteria and not to violate any of the exclusion criteria will be randomized at baseline (visit 2) to receive treatment with either brodalumab or placebo. Treatment assignment will be according to a computer generated randomization (REDCap, <https://redcap.au.dk>) in a 1:1 ratio. The method of randomization will be based on matched pairs design in which subjects will be matched on sex and age stratification (age decades; 40 – 49, 50 – 59, 60 – 69, 70 – 79, > 80).

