15.1 Sample size

Derived from our investigations of vascular inflammation in psoriasis patients and control subjects, we expect a mean aortic TBR_{max} of 2.4 with a standard deviation of 0.35 in the psoriasis subjects. After successful treatment with biologic agents, we expect the MeanTBR_{max} in the psoriasis subjects to be reduced to 2.1 with SD 0.35. Based on these assumptions and an alpha-level of 0.05 we calculate that 22 psoriasis subjects in each study arm will provide a power of 80% to detect a difference between the groups. By choosing a sample size of 25 psoriasis subjects we allow for a dropout of 3 subjects at follow-up without reducing power significantly.

Trial ID (EudraCT No.): 2017-003697-14	Date: 23.02.2018	Page Version 2.3
---	------------------	---------------------

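### Randomisation is matched on sex and age, but the protocol puts both factors in a conditional supportive analysis instead of the primary model; naming them there would be a nearly free gain in precision

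*Protocol*

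**What the plan says.** Protocol section 10.1 states: "Subjects are randomized and matched on sex and age". It gives an age tolerance of 5 years either way and calls the scheme stratified randomisation. Section 12.3 states: "The method of randomization will be based on matched pairs design in which subjects will be matched on sex and age stratification", with age grouped in decades.

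For the primary endpoint, the change in MeanTBRmax of the entire aorta from baseline to week 16, section 15.4.1 says: "The endpoint will be analysed using a repeated measurements model". It names no sex, age, stratum or pair term. Age and gender come in only afterwards, alongside body mass index, statin treatment and smoking: "If applicable, a supportive multivariate analysis will be performed to test the effect of the continuous covariates age, body mass index". Section 15.4.2 specifies the same type of model for SLR and the aortic subsegments and refers to the same supportive analysis.

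The sample size in section 15.1 is a plain two-group comparison that takes no credit for the matching.

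**The concern.** When arms are balanced on a factor by design, the variation due to that factor is removed from the treatment contrast. A model that omits the factor leaves the same variation in the residual, so the reported standard error is larger than the true one. Confidence intervals are then wider than the design warrants, and the precision that matching could buy is not used. With about 22 evaluable subjects per arm, even a small gain is worth having.

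This is more than a detail left for the SAP, which is not at hand. The protocol assigns the two factors it randomises on to a supportive analysis that may or may not be run, together with covariates that played no part in allocation.

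**Working it through.** **Inputs from the protocol.** Section 15.1: means 2.4 and 2.1 (difference 0.30), SD 0.35 in both groups, alpha 0.05, 22 per arm for 80% power, 25 per arm with dropout. Section 15.4.1: two-sided test. Not given: R2, here the share of the variance of the analysed outcome that sex and age explain. It is varied below as an assumption. The SD of 0.35 is stated for a level at one time; using it for the change is also an assumption, and is exact when the correlation between visits is 0.5, because 0.35 x sqrt(2 x (1 - 0.5)) = 0.35.

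**Reproducing the plan.** n per arm = 2 x (1.960 + 0.842)^2 x (0.35/0.30)^2 = 2 x 7.85 x 1.361 = 21.4, rounded up to 22, which matches. Power at 22 per arm is 81.1% by the normal approximation and 79.3% by the noncentral t.

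**Effect of omitting the factors.** With exact balance and n per arm:

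- true variance of the difference = 2 x SD^2 x (1 - R2)/n
- variance that the unadjusted model estimates = about 2 x SD^2/n
- ratio of standard errors = 1/sqrt(1 - R2)

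At n = 22 the unadjusted SE is 0.35 x sqrt(2/22) = 0.1055. At R2 = 0.10 the true SE is 0.1055 x sqrt(0.90) = 0.1001, so the unadjusted one is 1.054 times too large.

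**Power and type I error at 22 per arm, difference 0.30.** The adjusted column is a noncentral t with SD x sqrt(1 - R2) and 42 - 2 = 40 degrees of freedom. The unadjusted columns come from 50,000 simulated trials of 22 matched pairs analysed with an unpaired t-test.

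| Assumed R2 | SE factor | Adjusted power | Unadjusted power | Unadjusted type I error |
|---|---|---|---|---|
| 0 | 1.00 | 79.2% | 79.3% | 5.0% |
| 0.05 | 1.026 | 81.2% | 79.9% | 4.45% |
| 0.10 | 1.054 | 83.2% | 80.4% | 4.1% |
| 0.20 | 1.118 | 87.3% | 81.6% | 3.1% |

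Adjustment gains about -0.1, 1.3, 2.8 and 5.7 points.

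**Which R2 is plausible.** The outcome is a change, so an age or sex effect of equal size at both visits subtracts out and R2 for a pure change is zero. If baseline is instead used as a covariate, a little remains. Let s be the share of variance that sex and age explain at each visit and r the correlation between visits. Then the remaining share is 1 - [(1 - s) - (r - s)^2/(1 - s)]/(1 - r^2). For an assumed r = 0.7 and s = 0.10: (1 - s) - (0.6)^2/0.9 = 0.90 - 0.40 = 0.50; 0.50/0.51 = 0.980; remaining share 2.0%. For s = 0.05, 0.10 and 0.20 the results are 0.9%, 2.0% and 4.4% at r = 0.7, and 1.8%, 3.7% and 8.3% at r = 0.5. Most of these lie below the 0.05 row of the table.

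**Pair terms as an alternative.** In the same simulation a paired t-test has 77.5% power at R2 = 0 and 79.4% at 0.05, against 79.3% and 79.9% unpaired. Pair terms cost more than they return in the plausible range.

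**The case against.** The strongest reply is that nothing here is invalid. The unadjusted test is conservative, no bias arises, and section 15.1 promised 80% from an unadjusted comparison, which it still delivers. That stands. A reader might infer that the trial is underpowered or that its type I error is wrong in the harmful direction; the table shows neither.

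It is also fair to say that any loss is conditional. It requires sex and age to predict the change, not merely the level, of FDG uptake, and the documents give no figure for that. So it cannot be stated that power will be lost, only that it may be. The simulation further assumes 22 intact and exactly balanced pairs. Matching by decade is coarse, and the per-protocol exclusions in section 15.2 will break some pairs, so the overstatement of the SE would be smaller in practice.

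Third, section 15.4.1 lists no model terms at all, and an SAP could add these two. This carries less weight, because the protocol does say where age and gender go, and that is the supportive analysis.

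Finally, a reader might take the supportive analysis to use a different outcome, since its text speaks of a difference at week 16. That wording can equally mean the treatment difference in change, so it needs clarifying but is not a demonstrated contradiction.

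**Conclusion.** The mismatch between allocation and analysis is in the text, and its direction is clear: standard errors too large, test conservative. Its size depends on an unknown R2 for the change. At 0.05 or below, the more plausible range given that time-constant effects cancel, adjustment gains about 1 point of power or less; at 0.10 about 3 points and at 0.20 about 6. If sex and age turn out not to be prognostic, adjusting costs about 0.1 point. This is an efficiency improvement worth making because it is almost free, and it does not challenge the validity of the planned test or its stated 80% power.

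A separate, smaller matter is that sections 10.1 and 12.3 describe the matching differently (within 5 years against age decades). The rule determines which age term mirrors the allocation, so the two need to agree.

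**What to change.** In sections 15.4.1 and 15.4.2, and in the SAP, include sex and age at randomisation as prespecified fixed effects in the repeated measurements model, each with its effect on the week-16 change (for example through an interaction with visit). Report that adjusted treatment difference as the main result for MeanTBRmax, SLR and the subsegments. Use covariate or stratum terms rather than pair terms, because per-protocol exclusions break pairs. Sex plus continuous age is the cheapest choice and works under either matching rule.

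Reconcile sections 10.1 and 12.3 on the matching rule. Keep body mass index, statin use and smoking for the supportive model, and state that it uses the same change outcome as the primary analysis.

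The cost is a few sentences and about 2 degrees of freedom. Sex and month and year of birth are already recorded under section 13.2.1. The change should be made before unblinding.
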